5.2 SAFETY PARAMETERS AND DEFINITIONS

Safety assessments will consist of monitoring and recording adverse events, including serious adverse events and adverse events of special interest, performing protocol-specified safety laboratory assessments, measuring protocol-specified vital signs, and conducting other protocol-specified tests that are deemed critical to the safety evaluation of the study.

Certain types of events require immediate reporting to the Sponsor, as outlined in Section 5.4.

5.2.1 Adverse Events

According to the ICH guideline for Good Clinical Practice, an adverse event is any untoward medical occurrence in a clinical investigation patient administered a pharmaceutical product, regardless of causal attribution. For patients in the observation arm, an adverse event is any untoward medical occurrence. An adverse event can be any of the following:

- Any unfavorable and unintended sign (including an abnormal laboratory finding), symptom, or disease temporally associated with the use of a medicinal product, whether it is considered related to the medicinal product or not
- Any new disease or exacerbation of an existing disease (a worsening in the character, frequency, or severity of a known condition), except as described in Section 5.3.5.10.
- Recurrence of an intermittent medical condition (e.g., headache) not present at baseline
- Any deterioration in a laboratory value or other clinical test (e.g., ECG, X-ray) that is associated with symptoms or leads to a change in study treatment or concomitant treatment or discontinuation from study drug
- Adverse events that are related to a protocol-mandated intervention, including those that occur prior to assignment of study treatment (e.g., screening invasive procedures such as biopsies)
- Late complications related to surgery (e.g., urinary infection, intestinal obstruction, wound dehiscence, anastomotic leak or stricture)

5.2.2 Serious Adverse Events (Immediately Reportable to the Sponsor)

A serious adverse event is any adverse event that meets any of the following criteria:

- Is fatal (i.e., the adverse event actually causes or leads to death)
- Is life threatening (i.e., the adverse event, in the view of the investigator, places the patient at immediate risk of death)

This does not include any adverse event that had it occurred in a more severe form or was allowed to continue might have caused death.

- Requires or prolongs inpatient hospitalization (see Section 5.3.5.11)
- Results in persistent or significant disability/incapacity (i.e., the adverse event results in substantial disruption of the patient's ability to conduct normal life functions)
- Is a congenital anomaly/birth defect in a neonate/infant born to a mother exposed to study drug

- Is a significant medical event in the investigator's judgment (e.g., may jeopardize the patient or may require medical/surgical intervention to prevent one of the outcomes listed above)

The terms "severe" and "serious" are not synonymous. Severity refers to the intensity of an adverse event (e.g., rated as mild, moderate, or severe, or according to National Cancer Institute Common Terminology Criteria for Adverse Events (NCI CTCAE) criteria; see Section 5.3.3); the event itself may be of relatively minor medical significance (such as severe headache without any further findings).

Severity and seriousness need to be independently assessed for each adverse event recorded on the eCRF.

Serious adverse events are required to be reported by the investigator to the Sponsor immediately (i.e., no more than 24 hours after learning of the event; see Section 5.4.2 for reporting instructions).

5.2.3 Adverse Events of Special Interest (Arm A Only; Immediately Reportable to the Sponsor)

For patients in the atezolizumab treatment arm (Arm A), adverse events of special interest are required to be reported by the investigator to the Sponsor immediately (i.e., no more than 24 hours after learning of the event; see Section 5.4.2 for reporting instructions). Adverse events of special interest for this study include the following:

- Cases of potential drug-induced liver injury that include an elevated ALT or AST in combination with either an elevated bilirubin or clinical jaundice, as defined by Hy's law (see Section 5.3.5.7)
- Suspected transmission of an infectious agent by the study drug, as defined below:

Any organism, virus, or infectious particle (e.g., prion protein transmitting transmissible spongiform encephalopathy), pathogenic or non-pathogenic, is considered an infectious agent. A transmission of an infectious agent may be suspected from clinical symptoms or laboratory findings that indicate an infection in a patient exposed to a medicinal product. This term applies only when a contamination of the study drug is suspected.
- Pneumonitis
- Colitis
- Endocrinopathies: diabetes mellitus, pancreatitis, adrenal insufficiency, hypothyroidism and hypophysitis
- Hepatitis, including AST or ALT > 10 × ULN
- Systemic lupus erythematosus
- Neurological disorders: Guillain-Barre syndrome, myasthenic syndrome or myasthenia gravis, meningoencephalitis
- Nephritis

- Events suggestive of hypersensitivity, infusion-related reactions, cytokine-release syndrome, influenza-like illness, and systemic inflammatory response syndrome
- Ocular toxicities (e.g., uveitis, retinitis, optic neuritis)
- Myositis
- Myopathies, including rhabdomyolysis
- Grade ≥ 2 cardiac disorders (e.g., atrial fibrillation, myocarditis, pericarditis)
- Vasculitis
- Autoimmune hemolytic anemia
- Severe cutaneous reactions (e.g., Stevens-Johnson syndrome, dermatitis bullous, toxic epidermal necrolysis)

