5.1.1 Risks Associated with Atezolizumab

Atezolizumab has been associated with risks such as the following: IRRs and immune-mediated hepatitis, pneumonitis, colitis, pancreatitis, diabetes mellitus, hypothyroidism, hyperthyroidism, adrenal insufficiency, hypophysitis, Guillain-Barré syndrome, myasthenic syndrome or myasthenia gravis, meningoencephalitis, myocarditis, nephritis, and myositis. Immune-mediated reactions may involve any organ system and may lead to hemophagocytic lymphohistiocytosis and macrophage activation syndrome (considered to be potential risks for atezolizumab). Refer to [Appendix 9](#) of the protocol and Section 6 of the Atezolizumab Investigator's Brochure for a detailed description of anticipated safety risks for atezolizumab (see [Appendix 6](#) for precautions for anaphylaxis).

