5.3.1 Adverse Event Reporting Period

Investigators will seek information on adverse events at each patient contact. All adverse events, whether reported by the patient or noted by study personnel, will be recorded in the patient’s medical record and on the Adverse Event eCRF.

After informed consent has been obtained **but prior to initiation of study drug** for patients in Arm A or prior to the Cycle 1, Day 1 visit for patients in Arm B, only serious adverse events caused by a protocol-mandated intervention (e.g., invasive procedures such as biopsies, discontinuation of medications) should be reported (see Section 5.4.2 for instructions for reporting serious adverse events).

For patients in Arm A, after initiation of study drug, all serious adverse events and adverse events of special interest, regardless of relationship to study drug, will be reported until 90 days after the last dose of study drug or until the initiation of another anti-cancer therapy, whichever occurs first. All other adverse events, regardless of relationship to study drug, will be reported until 30 days after the last dose of study drug or until the initiation of another anti-cancer therapy, whichever occurs first.

For patients in Arm B, all adverse events occurring from the date of the Cycle 1, Day 1 visit until 30 days after the last day of the observation period or until the start of an anti-cancer therapy (whichever occurs first) will be reported.

Instructions for reporting adverse events that occur after the adverse event reporting period are provided in Section 5.6.

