Risks Associated with Atezolizumab and Guidelines for Management of Adverse Events Associated with Atezolizumab (cont.)

Table 4 Management Guidelines for Endocrine Events

Event	Management
Asymptomatic hypothyroidism	
 • Continue atezolizumab. • Initiate treatment with thyroid replacement hormone. • Monitor TSH weekly.
Symptomatic hypothyroidism	
 • Withhold atezolizumab. • Initiate treatment with thyroid replacement hormone. • Monitor TSH weekly. • Consider patient referral to endocrinologist. • Resume atezolizumab when symptoms are controlled and thyroid function is improving.
Asymptomatic hyperthyroidism	
TSH \geq 0.1 mU/L and $<$ 0.5 mU/L:
 
 • Continue atezolizumab. • Monitor TSH every 4 weeks. 
TSH $<$ 0.1 mU/L:
 
 • Follow guidelines for symptomatic hyperthyroidism.
Symptomatic hyperthyroidism	
 • Withhold atezolizumab. • Initiate treatment with anti-thyroid drug such as methimazole or carbimazole as needed. • Consider patient referral to endocrinologist. • Resume atezolizumab when symptoms are controlled and thyroid function is improving. • Permanently discontinue atezolizumab and contact Medical Monitor for life-threatening immune-mediated hyperthyroidism. ^c

MRI = magnetic resonance imaging; TSH = thyroid-stimulating hormone.

- ^a Atezolizumab may be withheld for a longer period of time (i.e., > 12 weeks after event onset) to allow for corticosteroids (if initiated) to be reduced to \leq 10 mg/day oral prednisone or equivalent. The acceptable length of the extended period of time must be agreed upon by the investigator and the Medical Monitor.
- ^b If corticosteroids have been initiated, they must be tapered over \geq 1 month to \leq 10 mg/day oral prednisone or equivalent before atezolizumab can be resumed.
- ^c Resumption of atezolizumab may be considered in patients who are deriving benefit and have fully recovered from the immune-mediated event. Patients can be re-challenged with atezolizumab only after approval has been documented by both the investigator (or an appropriate delegate) and the Medical Monitor.

Appendix 9

Risks Associated with Atezolizumab and Guidelines for Management of Adverse Events Associated with Atezolizumab (cont.)

Table 4 Management Guidelines for Endocrine Events (cont.)

Event	Management

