4.5.2 Adverse Events

Verbatim descriptions of adverse events will be mapped to Medical Dictionary for Regulatory Activities (MedDRA terms). Treatment emergent events (defined as events occurring on or after the first dose of atezolizumab, or, for patients in the observation arm, after the date of randomization) will be summarized by MedDRA term, appropriate MedDRA levels, and NCI CTCAE (National Cancer Institute, Common Terminology Criteria for Adverse Events) v4.0 grade. For each patient, multiple occurrences of the same event will be counted once at maximum severity reported will be used in the summaries. Adverse events will be summarized regardless of relationship to study drug as assessed by the investigator. All adverse events, adverse events leading to withdrawal of study drug, adverse events leading to dose interruption, Grade ≥ 3 adverse events, serious adverse events, adverse events related to study drug, adverse events of special interest, and immune-mediated adverse events will be summarized. Deaths and cause of death will be summarized.

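### Hyperthyroidism is a named atezolizumab risk but, unlike hypothyroidism, is not on the AESI list, and no reason is given; non-serious cases are therefore reported, collected and tabulated differently

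*Protocol*

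**What the plan says.** Protocol 5.1.1, listing the risks associated with atezolizumab, includes the run "pancreatitis, diabetes mellitus, hypothyroidism, hyperthyroidism, adrenal insufficiency, hypophysitis". The two thyroid disorders stand side by side.

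Protocol 5.2.3 defines the AESIs for Arm A. It opens with "Adverse events of special interest for this study include the following" and has one endocrine entry: "Endocrinopathies: diabetes mellitus, pancreatitis, adrenal insufficiency, hypothyroidism and hypophysitis". No other entry in the list covers hyperthyroidism.

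Appendix 9, Table 4 has separate rows for asymptomatic and symptomatic hyperthyroidism. The symptomatic row contains a hold, the instruction "Initiate treatment with anti-thyroid drug such as methimazole or carbimazole as needed", a condition for resuming, and "Permanently discontinue atezolizumab and contact Medical Monitor for life-threatening immune-mediated hyperthyroidism".

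Protocol 5.3.1 sets the Arm A collection periods. Serious events and AESIs are collected to 90 days after the last dose. For the rest, "All other adverse events, regardless of relationship to study drug, will be reported until 30 days after the last dose of study drug". Either period ends earlier if another anti-cancer therapy starts. Protocol 5.2.3 and 5.4 put AESIs on a 24-hour reporting clock.

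Protocol 6.5 plans an AESI summary. SAP 4.5.2 repeats it and adds a further category: "adverse events of special interest, and immune-mediated adverse events will be summarized". The SAP gives no term list for either.

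**The concern.** The AESI label is not only a heading in a table. For a non-serious event in Arm A it decides how fast the sponsor hears of it, how long sites go on collecting it, and whether it is counted in the AESI summary. If the label is given to an underactive thyroid and not to an overactive one, the AESI summary shows one direction of thyroid dysfunction only. The two directions are also observed for different lengths of time after treatment, so their rates cannot be compared on equal terms. At stake is the completeness of a safety display in one arm; no efficacy result depends on it.

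**Working it through.** There is no planned figure to reproduce; the check is a comparison of texts plus one subtraction.

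**1. Is hyperthyroidism the exception?** Protocol 5.1.1 names 16 associated risks: infusion-related reactions, hepatitis, pneumonitis, colitis, pancreatitis, diabetes mellitus, hypothyroidism, hyperthyroidism, adrenal insufficiency, hypophysitis, Guillain-Barré syndrome, myasthenic syndrome or myasthenia gravis, meningoencephalitis, myocarditis, nephritis and myositis. Set against 5.2.3, 15 of the 16 appear (myocarditis only through the Grade 2 or higher cardiac entry). Hyperthyroidism is the one that does not. Section 5.1.1 also mentions hemophagocytic lymphohistiocytosis and macrophage activation syndrome, as potential risks; these are not on the AESI list either.

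**2. Is the endocrine entry open or closed?** The lead-in to the list is not expressly exhaustive. The endocrine entry, however, is five terms after a colon with no marker of example, whereas the ocular, cardiac and cutaneous entries in the same list are given as examples. A site would reasonably read the endocrine entry as fixed.

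**3. What changes for a non-serious Arm A case?**

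| | Hypothyroidism | Hyperthyroidism |
|---|---|---|
| Named risk (5.1.1) | yes | yes |
| Own rows in Appendix 9, Table 4 | yes | yes |
| AESI (5.2.3) | yes | no |
| 24-hour report (5.2.3, 5.4) | yes | no |
| Routine collection after last dose (5.3.1) | 90 days | 30 days |
| AESI summary (Protocol 6.5, SAP 4.5.2) | yes | no |

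The difference in collection is 90 − 30 = 60 days, that is, days 31 to 90. The last row assumes that the AESI table follows the list in 5.2.3, since the SAP states no other rule.

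**4. What is actually lost within those 60 days?**

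- Appendix 1 schedules thyroid function tests in Arm A at screening, at Cycle 5 and every four cycles after that, and at the discontinuation visit. The column heading and Protocol 4.5.13.3 place that visit no more than 30 days after the last dose, and no thyroid test is scheduled in follow-up. The last scheduled test therefore falls inside the shorter window. (Footnote a of Appendix 1 instead counts from the decision to stop, so after a long hold the visit could come later than day 30.)
- A serious case keeps the 24-hour report and the 90-day window whatever its AESI status.
- Under Protocol 5.1.2.2, drug-related events still ongoing when treatment ends are followed until they resolve or stabilise, or until one of the other listed end points.
- Appendix 1, footnote x asks for later events of concern if they are judged related. Protocol 5.6 is narrower: apart from deaths, it covers only related serious events.

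What remains is new, non-serious hyperthyroidism with onset on days 31 to 90, found through symptoms or an unscheduled test and not volunteered under footnote x.

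**5. What is merely displayed elsewhere?** Non-serious cases up to day 30 are on the Adverse Event eCRF. They appear in the all-event tables and, where they qualify, in the tables for interruption, withdrawal, Grade 3 or higher, and drug-related events. They may also appear in the SAP's immune-mediated summary. That summary cannot show events that were never collected.

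**The case against.** The strongest reply is that the three sections have different jobs: 5.1.1 describes risks, Appendix 9 guides management, and 5.2.3 selects events for expedited reporting. Nothing says that the third must mirror the other two. Other events with hold or stop instructions in Appendix 9 are also not named as AESIs, for example Grade 2 immune-mediated neuropathy, Grade 3 or 4 hyperglycemia, and Grade 3 or 4 amylase or lipase elevation. This stands. A reader might infer that the protocol contradicts itself; it does not, and the omission may be deliberate. What is missing is a reason, given that the other thyroid disorder is on the list.

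A second reply is that the permanent-discontinuation instruction shows no reporting gap, because it concerns life-threatening disease, which is serious by the definition in 5.2.2. This also stands. The gap concerns non-serious cases only.

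A third is that the list is open-ended through its lead-in. This is weaker, for the reason given in step 2 of the working. If the entry was meant to be open, sites need to be told so, or about 200 of them may flag cases differently.

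A fourth is that the SAP's immune-mediated summary and footnote x already cover the matter. They help in part. The first has no stated terms, and the second depends on the investigator's judgement and carries no 24-hour clock.

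**Conclusion.** The point holds as a low-severity inconsistency in safety reporting, confined to non-serious events in Arm A. Followed as written, the plan gives an AESI summary that includes hypothyroidism and omits hyperthyroidism, with routine collection of the two differing by 60 days after the last dose. This rests on reading the endocrine entry as fixed and on the AESI table following 5.2.3.

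A reader might go further and conclude that all non-serious hyperthyroidism is lost, or might multiply an assumed incidence by the roughly 400 patients in Arm A (800 / 2) to obtain a number of missing patients. The documents support neither step. They give no incidence, and such a product would mostly count patients absent from one table but recorded in others. The number with new onset on days 31 to 90, the only real loss of data, cannot be derived from the documents. The DFS and OS analyses are unaffected.

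**What to change.** In the protocol, reconcile 5.1.1, 5.2.3 and Appendix 9 so that the AESI reporting list treats both directions of thyroid dysfunction in the same way, or state why hyperthyroidism is excluded. This concerns the reporting list only; no change to any management instruction is proposed.

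In the SAP, define how AESIs are derived. Include in the endocrine group the hyperthyroidism terms already recorded on the Adverse Event eCRF, whether or not the site flagged them. Add a note to the table that non-serious cases beyond 30 days after the last dose may be under-collected.

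The cost is a one-line protocol change, one added term group and a few more expedited reports. The protocol change works only forward: treatment lasts at most one year, so for patients already more than 90 days past their last dose it recovers nothing. The SAP change is useful whatever the timing, but it can count only what was collected.

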5.3 METHODS AND TIMING FOR CAPTURING AND ASSESSING SAFETY PARAMETERS

The investigator is responsible for ensuring that all adverse events (see Section 5.2.1 for definition) are recorded on the Adverse Event eCRF and reported to the Sponsor in accordance with instructions provided in this section and in Sections 5.4–5.6.

For each adverse event recorded on the Adverse Event eCRF, the investigator will make an assessment of seriousness (see Section 5.2.2 for seriousness criteria), severity (see Section 5.3.3), and causality (see Section 5.3.4).

5.3.1 Adverse Event Reporting Period

Investigators will seek information on adverse events at each patient contact. All adverse events, whether reported by the patient or noted by study personnel, will be recorded in the patient’s medical record and on the Adverse Event eCRF.

After informed consent has been obtained **but prior to initiation of study drug** for patients in Arm A or prior to the Cycle 1, Day 1 visit for patients in Arm B, only serious adverse events caused by a protocol-mandated intervention (e.g., invasive procedures such as biopsies, discontinuation of medications) should be reported (see Section 5.4.2 for instructions for reporting serious adverse events).

For patients in Arm A, after initiation of study drug, all serious adverse events and adverse events of special interest, regardless of relationship to study drug, will be reported until 90 days after the last dose of study drug or until the initiation of another anti-cancer therapy, whichever occurs first. All other adverse events, regardless of relationship to study drug, will be reported until 30 days after the last dose of study drug or until the initiation of another anti-cancer therapy, whichever occurs first.

For patients in Arm B, all adverse events occurring from the date of the Cycle 1, Day 1 visit until 30 days after the last day of the observation period or until the start of an anti-cancer therapy (whichever occurs first) will be reported.

Instructions for reporting adverse events that occur after the adverse event reporting period are provided in Section 5.6.

5.3.2 Eliciting Adverse Event Information

A consistent methodology of non-directive questioning should be adopted for eliciting adverse event information at all patient evaluation timepoints. Examples of non-directive questions include the following:

"How have you felt since your last clinic visit?"

"Have you had any new or changed health problems since you were last here?"

5.3.3 Assessment of Severity of Adverse Events

The adverse event severity grading scale for the NCI CTCAE v4.0 will be used for assessing adverse event severity. Table 8 will be used for assessing the severity for adverse events that are not specifically listed in the NCI CTCAE.

Table 8 Adverse Event Severity Grading Scale

Grade	Severity
1	Mild; asymptomatic or mild symptoms; clinical or diagnostic observations only; or intervention not indicated
2	Moderate; minimal, local, or non-invasive intervention indicated; or limiting age-appropriate instrumental activities of daily living ^a
3	Severe or medically significant, but not immediately life threatening; hospitalization or prolongation of hospitalization indicated; disabling; or limiting self-care activities of daily living ^{b, c}
4	Life-threatening consequences or urgent intervention indicated ^d
5	Death related to adverse event ^d

NCI CTCAE = National Cancer Institute Common Terminology Criteria for Adverse Events.

Note: On the basis of the NCI CTCAE (Version 4.0), which can be found at:

http://evs.nci.nih.gov/ftp1/CTCAE/CTCAE_4.03_2010-06-14_QuickReference_8.5x11.pdf

- ^a Instrumental activities of daily living refer to preparing meals, shopping for groceries or clothes, using the telephone, managing money, etc.
- ^b Examples of self-care activities of daily living include bathing, dressing and undressing, feeding one's self, using the toilet, and taking medications, as performed by patients who are not bedridden.
- ^c If an event is assessed as a "significant medical event," it must be reported as a serious adverse event (see Section 5.4.2 for reporting instructions), per the definition of serious adverse event in Section 5.2.2.
- ^d Grade 5 events must be reported as serious adverse events (see Section 5.4.2 for reporting instructions), per the definition of serious adverse event in Section 5.2.2.

